## Clinical Performance of Masimo Rad-GT

### 1. OVERALL SYNOPSIS OF THE CLINICAL INVESTIGATION

Clinical investigation title:	Clinical Performance of Masimo Rad-GT
Study objective(s):	To validate the performance of Masimo Rad-GT.
Investigational device(s):	Masimo Rad-GT
Number of participants:	Approximately 73 subjects.
Inclusion criteria:	Refer to section 6.3.1
Exclusion criteria:	Refer to section 6.3.2
Duration of the clinical investigation:	The expected duration of study enrollment is 1 to 3 months.
Study endpoint(s):	Accuracy of temperature measurements using the Masimo Rad-GT will be compared to reference temperature measurements

### 2. IDENTIFICATION AND DESCRIPTION OF THE INVESTIGATIONAL DEVICE

Masimo Corporation is the developer of noninvasive technologies for the measurement and monitoring of physiological variables, such as arterial oxygen saturation (SpO2), total hemoglobin concentration (SpHb), carboxyhemoglobin concentration (SpCO), methemoglobin concentration (SpMet), and other physiological variables to improve patient outcomes and reduce cost of care.

The Masimo Rad-GT device (see **Figure 1**) is a non-contact infrared thermometry device intended to ascertain body temperature from skin temperature measurements. Non-contact infrared thermometers utilize infrared sensors that detect thermal radiation from the body. The sensor then converts radiant energy to an electrical signal and provides a temperature reading without discomfort for the patient or associated hygiene concerns. Thus, non-contact thermometry is a particularly attractive solution due to its optimization of patient comfort, noninvasiveness, and minimization of cross contamination. The device is a non-invasive, non-contact, handheld pulse oximetry device with a rechargeable battery and LCD display. It uses Masimo Measure-through Motion and Low Perfusion™ SET® pulse oximetry technology to measure SpO2, respiration rate from the Pleth (RRp™), pulse rate (PR), perfusion index (PI), and temperature. The Masimo Rad-GT is not FDA cleared and is considered investigational. Though the Rad-GT may be used to measure the aforementioned parameters, the Rad-GT used in this study will only be used to measure body temperature.

**Figure 2** Masimo Rad-GT with integrated infrared temperature sensor at back of the device

# CLINICAL INVESTIGATION PLAN

## Clinical Performance of Masimo Rad-GT

### 3. JUSTIFICATION FOR THE DESIGN OF THE CLINICAL INVESTIGATION

This is a prospective, nonrandomized, single arm study wherein all subjects are enrolled into the experimental arm and will have their temperature taken with Masimo Rad-GT. The study is designed to validate the clinical performance of Masimo Rad-GT in the accuracy of temperature measurements.

### 4. BENEFITS AND RISKS OF THE INVESTIGATIONAL DEVICE, CLINICAL PROCEDURE, AND CLINICAL INVESTIGATION

#### 4.1. Anticipated Benefits

There will be no direct benefits to the enrolled participants; however, this study hopes to learn more about the temperature device to potentially help other patients in the future. Other possible benefits would be to society as a whole.

#### 4.2. Risks/Discomforts Associated with Participation in the Clinical Investigation

- Risks Associated with the Device

The Rad-GT device does not pose risks to the participant, because the device is non-contact and does not emit any energy. Reference measurements will be obtained using a [REDACTED] using normal practice.

- Risks from Inflicted Knowledge

The risk of inflicted medical knowledge to subjects is negligible since we de-identify all associated information including those relevant to our clinical and engineering parameter studies. The monitoring and test results are not examined for diagnostic purposes and do not reflect an attempt to ascertain any subject's medical condition. The attending physician's role during this study is to ensure the safety of the subject during the study.

We will reduce the risk of inflicted knowledge by assuring the subjects that device readings are for research use only. In the case that a subject becomes aware of a condition (hypertension, arrhythmia, etc.) they have during the course of our study, our study staff will recommend that they contact their primary care physician and we will document this recommendation. As part of that process, we will follow up with these individuals prior to enrollment if their condition meets exclusion criteria for a study.

- Risks from Loss of Confidentiality

Masimo upholds the highest standards to protect hard and electronic data, however, a complete promise for confidentiality cannot be guaranteed due to unforeseeable events.

#### 4.3. Importance of Knowledge Gained

Development of new temperature technologies could enable users to monitor temperature vital signs remotely and lessen the need for hospital visits.

#### 4.4. Emergency Response Plan for Medical Emergencies

A crash cart equipped with medications to provide immediate care during emergencies is on site and full emergency services are within 3 miles.

Study staff will dial 911 for medical emergencies that require emergency medical services (EMS) to be contacted.

#### 4.5. Alternatives

The alternative is to not participate in the study.

# CLINICAL INVESTIGATION PLAN

## Clinical Performance of Masimo Rad-GT

### 5. OBJECTIVES OF THE CLINICAL INVESTIGATION

The objective of this study is to validate Masimo Rad-GT to evaluate the performance of the device in obtaining temperature measurements. Measurements from the Masimo Rad-GT will be compared to [REDACTED].

### 6. DESIGN OF THE CLINICAL INVESTIGATION

#### 6.1. General

This is a prospective, nonrandomized, single arm study. Temperature data will be obtained using the Masimo Rad-GT while obtaining [REDACTED] as a reference.

Accuracy of temperature measurements using the Masimo Rad-GT will be compared to the [REDACTED].

The validation of the accuracy of the temperature measurement in the investigational device may be determined using data collected from this study, in addition to data from other Masimo sponsored studies.

#### 6.2. Equipment and Materials

Equipment and materials are to be used as required. All study personnel will be trained on the use of relevant equipment.

##### Investigational Device

- Masimo Rad-GT

##### Reference Equipment

- Hospital standard of care [REDACTED]

##### Research Equipment

- Laptop with data collection software

#### 6.3. Investigational device(s) and comparator(s)

The study will collect data to calibrate and validate the performance of the Masimo Rad-GT as compared to [REDACTED].

##### 6.3.1. Inclusion Criteria (Eligible Subjects)

- Subject is 18 to 80 years of age.
- Subjects are able to read and communicate in English as well as understand the study and the risks involved.

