#### Reference Measurements:

\* Measurements may be taken several times throughout the study.

(see Figure 3)

the hospital's standard of care. Multiple reference measurements may be obtained.

Data from [REDACTED] at the end of data collection for each subject.

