#### 7.3. Statistical Analysis

The statistical analysis will follow the procedure outlined in ISO 80601-2-56:2017 section 201.102.

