##### 7.3.1. Exclusion

Data from the following participants will be excluded from data analysis:

- Any subject administered antipyretic medications during study participation
- Any subject who does not complete at least one full round of measurements.
- Any subject whose data suggests a defective device or sensor.
- Any subject whose data suggests existence of external conditions that interfere with Rad-GT or reference measurements.

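### Should section 7.3 add an analysis of error against reference temperature because the eligibility text sets no temperature range?

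*Combined protocol and SAP*

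**What the plan says.** Section 6.3.1 has two inclusion criteria: "Subject is 18 to 80 years of age" and "Subjects are able to read and communicate in English as well as understand the study and the risks involved". Section 6.3.2 excludes pregnant or nursing subjects, certain neurological or psychiatric disorders, and others at the investigator's or staff's discretion. Neither list shows a redaction or mentions body temperature.

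The synopsis gives the endpoint as "Accuracy of temperature measurements using the Masimo Rad-GT will be compared to reference temperature measurements", and section 5 gives the objective as "to validate Masimo Rad-GT to evaluate the performance of the device in obtaining temperature measurements". Neither names a range. The analysis exclusion in 7.3.1 that comes nearest to fever is "Any subject administered antipyretic medications during study participation".

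The method in 7.3 is one sentence: "The statistical analysis will follow the procedure outlined in ISO 80601-2-56:2017 section 201.102". Section 7.2 takes the sample size of up to 73 from the same ISO section. Section 6.1 allows the validation to use this study's data "in addition to data from other Masimo sponsored studies". On the reference readings, section 6.4.3 says "Multiple reference measurements may be obtained".

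**The concern.** A thermometer matters most when temperature is raised. If nearly all subjects are afebrile, reference temperature hardly varies, and a device that compresses the scale can still show a mean error near zero and fairly narrow limits of agreement. Read as evidence of accuracy in general, such a result would reach further than the data.

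The visible text invites the worry. No criterion brings febrile subjects in, and the antipyretic exclusion may take some out. The setting is unclear: section 6.2 and the reference procedure in 6.4.3 use hospital wording, while 6.4.4 speaks of subjects returning to work. The temperature range of the other sponsor studies is not stated. A regression of (Rad-GT minus reference) on reference temperature, with the conclusion limited to the observed range, would cost little and need no extra subjects.

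**Working it through.** **Can the gap be established?** A range, a febrile quota or an analysis by temperature could sit in any of four places:

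- the ISO section cited in 7.2 and 7.3, which is not reproduced;
- the acceptance table in 7.1, of which only the header is visible;
- recruitment and phone screening (6.4.1), which are redacted, and parts of screening (6.4.2);
- the reference procedure in 6.4.3, which is broken in the public copy.

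No visible passage says that the output is a single pooled bias with limits of agreement. The sample size of 73 cannot be reproduced, because no alpha, power, SD, margin or dropout rate is given.

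**How large could the problem be?** Only N = 73 comes from the documents. Every other input below is an assumption.

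*Febrile subjects enrolled.* P(none) = (1 − p)^73, and the expected number is 73p.

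| Febrile share p | Expected | P(none) | P(at least 10) |
|---|---|---|---|
| 1% | 0.7 | 0.48 | <0.001 |
| 2% | 1.5 | 0.23 | <0.001 |
| 5% | 3.7 | 0.024 | 0.003 |
| 10% | 7.3 | 0.0005 | 0.19 |
| 20% | 14.6 | <0.0001 | 0.94 |
| 30% | 21.9 | <0.0001 | >0.99 |

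*What a compressing device would show.* Take device slope b, reference SD s and noise SD e. The SD of the difference is √(((1 − b)s)² + e²), and the limits of agreement are ±1.96 times that. Take b = 0.5 and e = 0.2 °C:

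- s = 0.3: √(0.15² + 0.2²) = 0.250, limits ±0.49 °C.
- s = 0.4: √(0.20² + 0.2²) = 0.283, limits ±0.55 °C.
- A device with b = 1: ±1.96 × 0.2 = ±0.39 °C.

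The compressing device's limits are about 25% to 40% wider. With a sample mean of 36.8 °C, its error at a true 38.5 °C is −0.5 × (38.5 − 36.8) = −0.85 °C. With e = 0.3 the limits are ±0.66 to ±0.71 against ±0.59 °C. With e = 0.4 they are ±0.84 to ±0.88 against ±0.78 °C.

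*What the regression would find in an afebrile sample.* The slope SE is e/(s√72). At e = 0.2 it is 0.079 (s = 0.3) or 0.059 (s = 0.4). Times t = 1.994 on 71 degrees of freedom, the 95% half-width is 0.16 or 0.12. The table gives the simulated share of studies whose upper 95% limit for the slope is below zero, for s = 0.3 to 0.4 (20,000 runs per cell).

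| True error slope | e = 0.2 | e = 0.3 | e = 0.4 |
|---|---|---|---|
| −0.5 | over 99% | 98% to over 99% | 87% to 98% |
| −0.3 | 96% to over 99% | 70% to 91% | 47% to 70% |
| −0.2 | 71% to 91% | 39% to 60% | 24% to 39% |
| −0.1 | 24% to 39% | 13% to 20% | 9% to 13% |

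*False slope from reference error.* With independent reference error SD r and m readings averaged, the induced slope is −(r²/m)/(s² + r²/m). For r = 0.1 °C it is −0.10 (s = 0.3) to −0.06 (s = 0.4) with one reading, and −0.05 to −0.03 with the mean of two.

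**The case for a change.** The strongest case for a change is that it helps whatever the hidden text says. If the ISO section already sets a range, one cited clause in 7.3 would tell the reader so. If it does not, the regression exposes a badly compressing device even in an afebrile sample, as the −0.5 row shows. It uses data already collected and alters neither recruitment nor sample size. Its only price is a possibly narrower claim, which would be the honest one.

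Much of this stands. The visible lists do lack a temperature range, the arithmetic is right under its assumptions, and the added analysis is sound. It is also true that wider limits give a compressing device away less clearly as noise grows.

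The step from useful to needed does not stand. Harm depends on few febrile subjects, a steep compression and a pooled-only analysis, and the documents support none of the three. The hospital wording and the antipyretic exclusion are at least as compatible with febrile subjects being present. The remedy mainly finds large slopes. In the feared afebrile sample, the upper temperature bands would be empty, and a slope of −0.1 could not be told from reference error. Nor does the plan claim accuracy beyond the range it observes.

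**Conclusion.** No change to the plan follows. The public text does not restate any temperature range or analysis by temperature that the incorporated standard may require. That is missing detail, not a shown error. Following the plan together with its ISO procedure is not shown to give a wrong result, and an addition cannot be shown to improve on a method that is not visible.

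The size is undetermined. The chance of enrolling no febrile subject runs from 48% to practically nil across assumed febrile shares of 1% to 30%. Whether a compressing device would pass cannot be said without the acceptance criterion. Analysts would sensibly plot error against reference temperature, averaging reference readings where there are several. They would also state the observed range for this study and separately for any pooled set. Citing the relevant ISO clause in 7.3 would be a courtesy to readers. This conclusion rests on treating redacted and incorporated text as part of the plan. If the standard and the hidden sections proved silent on temperature range, the question would be worth reopening.

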##### 6.3.2. Exclusion Criteria (Ineligible Subjects) (\* = Per study staff discretion)

- Subject is pregnant or nursing.
- Subject has a known neurological and/or psychiatric disorder (e.g., schizophrenia, bipolar disorder, Multiple Sclerosis, Huntington's disease) that interferes with the subject's level of consciousness. \*
- Subject has any medical condition which in the judgment of the investigator and/or study staff, renders them ineligible for participation in this study or subject is deemed ineligible by the discretion of the investigator/study staff.

#### 6.4. Procedures

### 6.4.1. Recruitment and Pre-Screening

#### 6.4.1.1. Advertisement and Recruitment

[REDACTED]

#### 6.4.1.2. Phone Screening

[REDACTED]

[REDACTED]

### 6.4.2. Consenting and Screening

[REDACTED]

[REDACTED]

[REDACTED]

The subject must read and sign the consent document, using our informed consent process.

The paper consent must be stamped with a current IRB approval. Due to the limitations of the electronic consent, the consent form may not be stamped with a current IRB approval; however, the IRB will review and approve the electronic document prior to implementation. The electronic consent will contain indicators that show the version of the form. No study-related activities will be conducted until consent is obtained from the subject.

After informed consent is obtained, subjects will be asked a brief series of health questions to ensure their eligibility for this study. Subjects who do not meet the inclusion criteria and/or meet exclusion criteria will not be eligible to participate in the study.

[REDACTED]

Body mass index (BMI) may also be calculated to assess for eligibility for the study.

## CLINICAL INVESTIGATION PLAN

### Clinical Performance of Masimo Rad-GT

Female subjects will be required to take a pregnancy test. Results will be noted. If the pregnancy test is positive, the subject will be removed from the study and notified of their pregnancy test results.

In addition, a medical history will be recorded after the initial screening questionnaire.

Subjects may be offered a snack (e.g., granola bar) and/or beverage (e.g., water, juice) due to the amount of time their involvement in this study may take.

#### 6.4.3. Data Collection Procedure

Data collected by the Rad-GT is not intended to be used for clinical decisions, and research personnel should continue to use standard of care procedures for monitoring participants.

Record subject demographic information such as, but not only limited to, age, gender, weight, height, Massey scale, race or ethnicity on the case report form (CRF), as well as current medical conditions and recent medical history.

Record start and end time of data collection procedures on the CRF.

#### Reference Measurements:

\* Measurements may be taken several times throughout the study.

(see Figure 3)

the hospital's standard of care. Multiple reference measurements may be obtained.

Data from [REDACTED] at the end of data collection for each subject.

#### Rad-GT Device Measurements:

\* Measurements may be taken several times throughout the study.

## Clinical Performance of Masimo Rad-GT

To obtain measurements using the Rad-GT device, start by locating the temperature button (**Figure 4a**) and sensor lens (**Figure 4b**). Make sure there are no obstructions to the sensor's field of view (i.e., hair, glasses, fingers, clothing).

### 6.4.4. Ending Procedure

At the conclusion of the procedure, the sensor(s)/device(s) will be removed (if applicable).  
The approximate subject participation is 1 hour.

All subjects will be encouraged to remain in the study area until they feel fit to leave. Subjects should feel safe and able before returning to work directly after participation in the study.

Subjects will be paid according to the compensation breakdown on the consent form.

## 6.5. Monitoring plan

A separate document for the study monitoring plan will be developed and followed to ensure subject safety

## Clinical Performance of Masimo Rad-GT

and GCP compliance.

### 7. STATISTICAL DESIGN AND ANALYSIS

#### 7.1. Acceptance Criteria

Parameter	Acceptance Criteria 

#### 7.2. Sample Size

The sample size of up to 73 participants per ISO 80601-2-56:2017, section 201.102.

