#### 7.4. Expected Dropout Rates

Participants may not complete the study for various reasons, at the investigator's or study staff's discretion, or because the participant does not want to continue the study. Due to the short duration and simple, noninvasive procedures of this study, there are limited expected dropouts.

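### Does giving the sample size as up to 73, with exclusions taken afterwards, leave the study too small or free to stop at will?

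*Combined protocol and SAP*

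**What the plan says.** Three places bear on the number of subjects.

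- Section 7.2 (Sample Size) is one line: "The sample size of up to 73 participants per ISO 80601-2-56:2017, section 201.102". The synopsis (Section 1) gives "Approximately 73 subjects". The first reads as a ceiling, the second as a target.
- Section 7.3.1 opens with "Data from the following participants will be excluded from data analysis" and lists four groups, among them "Any subject who does not complete at least one full round of measurements". Two of the four are identified from the data themselves (a suspected faulty device, or interfering external conditions). Section 6.4.2 adds a removal after consent: "If the pregnancy test is positive, the subject will be removed from the study".
- Section 7.4 gives no dropout rate; it says only that "there are limited expected dropouts", because the study is short and noninvasive. Section 6.4.4 puts participation at about one hour.

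The method is set by reference: "The statistical analysis will follow the procedure outlined in ISO 80601-2-56:2017 section 201.102". Section 6.1 adds that validation may draw on this study's data "in addition to data from other Masimo sponsored studies". The visible text has no inflation for losses, no replacement rule and no minimum evaluable number.

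**The concern.** A sample size taken from a standard is normally a number to be reached in the analysis. Here it is worded as a maximum, and subjects are then taken away from it. If 73 caps enrolment, 73 can be analysed only if 73 enrol and nobody is lost.

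The second worry is the missing floor. The study has one arm, no masking is described, and data reach the sponsor. If the final number may be anything up to 73, recruitment could end when the accuracy results look favourable without breaching Section 7.2. That would raise the chance that an inadequate device passes.

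**Working it through.** **The plan's own figure.** The 73 cannot be reproduced. The visible text gives no alpha, power, standard deviation or margin, the acceptance-criteria table in Section 7.1 shows no values, and the text of the standard is not in the documents. Whether the standard asks for 73, and whether enrolled or evaluable, therefore cannot be checked.

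**Expected loss.** Let d be the fraction excluded. The documents give no value, so the rates below are assumptions. If 73 is an enrolment cap:

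- expected analysed number = 73 × (1 − d)
- chance of fewer than 73 analysed = 1 − (1 − d)^73

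| d (assumed) | Expected analysed | Chance of fewer than 73 |
|---|---|---|
| 0% | 73 | 0% |
| 1% | 72.3 | 52% |
| 2% | 71.5 | 77% |
| 5% | 69.3 | 98% |
| 10% | 65.7 | above 99% |

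Some shortfall is likely at any of these rates above zero. What matters is its cost.

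**Cost in precision.** The half-width of the 95% confidence interval for mean bias, in units of the between-subject SD, is t(0.975, n − 1)/√n.

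| n | Calculation | Half-width (SD) | Relative to n = 73 |
|---|---|---|---|
| 73 | 1.9935/√73 | 0.233 | 1.00 |
| 70 | 1.9949/√70 | 0.238 | 1.02 |
| 69 | 1.9955/√69 | 0.240 | 1.03 |
| 66 | 1.9971/√66 | 0.246 | 1.05 |
| 65 | 1.9977/√65 | 0.248 | 1.06 |
| 30 | 2.0452/√30 | 0.373 | 1.60 |

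Losing three to eight subjects widens the interval by 2% to 6%. The 60% penalty at n = 30 applies only if 30 would comply with the plan. It complies with Section 7.2 read alone, but not with the synopsis.

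**Optional stopping.** This needs two inventions: a pass criterion and a schedule of looks. Suppose the device passes if its root-mean-square error (RMSE) is at or below a limit, and its true RMSE equals that limit. Simulation of 40,000 trials with normal errors gives:

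| Looks (assumed) | Pass rate |
|---|---|
| Once, at 73 | 52% |
| At 68 and 73 | 56% |
| At 60 and 73 | 59% |
| After each subject from 65 | 60% |
| After each subject from 30 | 77% |

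With a one-sided 5% test of the mean instead, looking after every subject from 30 gives about 14% to 15% false passes. The visible plan mentions neither RMSE, nor a one-sided test, nor any interim look. The last row is the extreme of a hypothetical range, not a property of this design.

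**The case for a change.** The best case for acting is that the clarification is nearly free. A few sentences would reconcile Sections 1 and 7.2, say whether 73 is enrolled or evaluable, state whether lost subjects are replaced, and tie the accuracy analysis to the end of enrolment. The statistical section, which should govern, is the one that uses the ceiling. Two exclusion groups are judged from the readings, so losses cannot be foreseen at recruitment. Case report forms are completed as the study runs, so accumulating results could be seen. The option of using other studies' data sets no minimum, since it is discretionary and carries no number or pooling rule.

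Most of this stands as description. The two phrases do differ, and the visible text has no replacement rule, though the recruitment and screening sections are partly blacked out. What does not stand is the step from loose wording to a defective design:

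- Section 7.2 speaks of participants without saying enrolled. It can equally be read as the analysed number, with losses replaced, and the synopsis leaves room for slightly more than 73.
- The claim that enrolment may stop at any number ignores the synopsis.
- A shortfall against the standard is unproven, because its requirement is not visible.
- The fear of data-driven stopping rests on conduct that the plan does not describe.

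**Conclusion.** The concern does not call for a change. The wording is imprecise, but the plan states no power, precision or evaluable number for the design to miss, and a study run as written with about 70 analysed would still support a sound conclusion on accuracy. The cost of the likely losses is an interval about 3% to 6% wider, assuming 5% to 10% excluded and mean bias as the quantity of interest; at 1% or 2% it is about 1% or less, since 1/√0.98 = 1.01. The remedies on offer are either a detail that a competent analyst supplies anyway (enrolled, excluded and analysed counts, with reasons) or a few more recruits for little gain.

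This rests on reading Section 7.2 together with the synopsis, so that the study aims at about 73. It would need to be revisited if the study closed far below that number, or if accuracy results were shown to have been reviewed while recruitment was still open.
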